#### 10.3 Meal Details

Meal details as recorded on the source workbook will be listed. Any recorded deviations from the planned meal times will be listed as protocol deviations.

#### 10.4 Adverse Events

Throughout the study, all AEs will be evaluated by the PI and noted in the AE section of the source workbook.

AEs will be coded using the Medical Dictionary for Regulatory Activities (MedDRA v21.0 (or most recent version), and reported by system organ class (SOC) and preferred term (PT).

AEs will be classified into the following categories:

- pre-dose AEs: AEs recorded at screening or with a start date and time prior to the first dose of IMP
- treatment-emergent adverse events (TEAEs): AEs that commence during/after the first dose of IMP (ie Period 1) or commence before first dose of IMP (ie a pre-dose AE or existing medical condition) but worsen in intensity during exposure to IMP or NIMP

į

Where the severity of a pre-dose AE intensifies during/after dosing of either IMP or NIMP this will be defined as a new AE and classified as a TEAE.

TEAEs will be assigned to the period in which the AE first occurred. Where the severity of an AE or symptom changes in a subsequent period, this will be defined as a new AE and included under the treatment associated with the subsequent period. AEs that occur during the washout period will be assigned to the treatment the subject received during the period immediately before the washout period.

AEs will be classified as "unrelated", "possibly related", and "related" when considering their relationship to IMP. TEAEs classified as "possibly related" and "related" will be defined as adverse drug reactions (ADRs). An ADR is any AE where a causal relationship with the IMP is at least a reasonable possibility ie "possibly related" or "related". Pre-dose AEs will always have the classification of "unrelated".

AEs will also be classified as "unrelated", "possibly related", and "related" when considering their relationship to NIMP.AEs will be classified as "mild," "moderate" or "severe" when considering their severity.

If the severity or relationship to IMP/NIMP of a TEAE is missing, the severity/relationship will be tabulated as "missing" in the summary tables.

Where the start date of an AE is missing and the stop date is on or after the day of first dose of IMP or both the start and stop dates are missing then a "worst-case" scenario will be assumed, ie the AE is assumed to have occurred post-dose and is therefore considered treatment-emergent. If a partial start date/time is available then the event will be considered as treatment-emergent unless the partial information suggests otherwise. The period to which the AE will be assigned will be hard coded using SAS Software and documented in a file note.

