14.5.6 Abnormal Laboratory Findings

In cases where laboratory findings are outside the normal range and the investigator believes that the results may be of clinical significance, repeat sampling may be requested as clinically indicated. If the abnormal finding is clinically significant, appropriate actions will be taken eg, the subject will not be entered into the study or the subject may be withdrawn from the study. The subject will be referred to their general practitioner or other appropriate provider for further care. The same will apply if the results of the HBsAg, HCV Ab or HIV test are positive and in addition the investigator will ensure that adequate counselling is available if requested.

Abnormal results at follow-up assessments will also require repeat testing if the investigator believes the results may be of clinical significance.

Any clinically significant abnormality, including changes from baseline, must be reported as an AE.

Additional blood and/or urine samples may be taken for safety tests. Furthermore, additional assays outside those specified in the protocol may be performed for safety reasons as requested by the investigator.

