#### 3.2.2 Definition of Treatments

KD025 (investigational medicinal product [IMP]), itraconazole (non-investigational medicinal product [NIMP]), rabeprazole (NIMP), rifampicin (NIMP) and omeprazole (NIMP) are referred to as study drugs in this Reporting and Analysis Plan (RAP).

Throughout the reporting of the study, period, day and treatments will be reported as detailed in Table 1 below.

Part	Period	Treatment Label	Day	IMP/NIMP Dose
	1	KD025 200 mg QD	Day 1	KD025 200 mg QD
	2	KD025 200 mg QD +	Day 3 (Period 1; or Day -7 of Period 2 if washout period is extended) and continuing from Day -6 to Day -1 (Period 2)	itraconazole 200 mg QD for 7 days
1			Day 1	KD025 200 mg QD + itraconazole 200 mg QD on 8 th day (ie Day 1)
			Day 2	itraconazole 200 mg QD on 9 th day (ie Day 2)
			Day -3 to Day -1	rabeprazole 20 mg BID for 3 days
	3	KD025 200 mg QD + rabeprazole	Day 1	KD025 200 mg QD + rabeprazole 20 mg QD on $4^{th}$ day (ie Day 1)
			Day -9 to Day -1	rifampicin 600 mg QD for 9 days
	4	KD025 200 mg QD + rifampicin	Day 1	KD025 200 mg QD on 10 th day (ie Day 1)
	1	KD025 200 mg BID	Day 1	KD025 200 mg BID (Q12h) on a single day
2	2	KD025 200 mg BID + omeprazole	Starting on Day 3 (Period 1, or Day -3 of Period 2 if washout period is extended) and continuing on Day -2 and Day -1 (Period 2)	omeprazole 20 mg QD for 3 days
			Day 1	KD025 200 mg BID (Q12h) on a single day + omeprazole 20 mg QD

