#### 10.4.1 Summary Tables for Adverse Events

All pre-dose AEs (as defined in Section 10.4) will be excluded from the summary tables but will be listed for all subjects.

Descriptive statistical methods will be used to summarise the TEAE data.

The number and percentage of subjects reporting each TEAE will be summarised for both SOC and PT. For summaries by SOC and PT, with the exception of TEAEs by severity and relationship to IMP, the number of subjects and the number of events will be summarised. For summaries by severity and relationship only the number of subjects will be summarised.

For counts of subjects experiencing events the following will apply:

- a subject experiencing TEAEs in more than one body system, within a study period, will be counted once in the total number of subjects with TEAEs in that study period;
- a subject with more than 1 TEAE in the same SOC, within a study period, counts only once at the SOC level;
- a subject with more than 1 TEAE in the same PT, within a study period, counts only once at the PT level.
For event counts, all events are included.

When it is necessary to calculate percentages, the denominator will be the total number of subjects in the safety dataset for that period (ie number of subjects dosed in each period, shown in TABLE 14.1.1.1

and the numerator will be the total number of subjects reporting a TEAE within the relevant category.

Summaries presented for SOC and PT will be presented in descending order of frequency overall ie most frequently reported SOC in the study and then by most frequently reported PT in the study within each SOC.

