TABLE 14.1.1.5 Extent of Exposure Summary Statistics: Safety Population Part 1: KD025 QD dosing

		Dose of KD025	Dose of	Dose of	Dose of
		200 mg QD	itraconazole	rabeprazole	rirampicin
TREATMENT	Day	n (%)	n (%)	n (%)	n (%)
KD025 200 mg QD (N=XX)	Day 1	xx (xx.x)			
KD025 200 mg QD + itraconazole (N=XX)	Day 3, Period 1 Day -6  Day -1 Day 1 Day 2	xx (xx.x)	xx (xx.x) xx (xx.x)  xx (xx.x) xx (xx.x) xx (xx.x)		
KD025 200 mg QD + rabeprazole (N=XX)	Day -3, Morning Day -3, Evening  Day -1, Morning Day -1, Evening Day 1	xx (xx.x)		xx (xx.x) xx (xx.x)  xx (xx.x) xx (xx.x) xx (xx.x)	
KD025 200 mg QD + rifampicin (N=XX)	Day -9  Day -1 Day 1	xx (xx.x)			xx (xx.x)  xx (xx.x)

Note: The data in this table are presented in listing x.x

All subjects are planned to receive KD025 200mg QD (IMP), all doses administered in the fed state Period 1: IMP; Period 2: 7 days itraconazole 200mg QD, IMP+itraconazole 200mg QD on 8th day, itraconazole 200mg QD on 9th day; Period 3: 3 days rabeprazole 20mg BID, IMP+rabeprazole 20mg QD on 4th day; Period 4: 9 days rifampicin 600mg QD, IMP on 10th day

PROGRAM PATH: X:\~\QSC200311\~\TFLS\PRODUCTION\TAB\_XX

DDMMMYYYY HH:MM

(Programming note: Continue this table for all periods and all days. If the minimum washout period is extended between Period 1 and Period 2, the first time-point for the second treatment may be changed from Day 3, Period 1 to Day -7, Period 2. A similar table will be produced for Part 2 [Table 14.1.2.5])

Reporting and Analysis Plan KD025-107 (QSC200311) Final v2.0 09 Nov 2018 Page 79 of 99

TABLE 14.1.1.6 Treatment Compliance for each NIMP Summary Statistics: Safety Population Part 1: KD025 QD dosing

Percentage of Compliance (%)	Itraconazole (N=XX)	Rabeprazole (N=XX)	Rifampicin (N=XX)
Mean	xx.xx	xx.xx	xx.xx
SD	xx.xx	xx.xx	、 xx • xx
Median	xx.xx	xx.xx	xx.xx
Min	xx.xx	xx.xx	xx.xx
Max	xx.xx	xx.xx	XX,XX
n	xx	XX	xx

Note: The data in this table are presented in listing x.x

All subjects are planned to receive KD025 200mg QD (IMP), all doses administered in the fed state Period 1: IMP; Period 2: 7 days itraconazole 200mg QD, IMP+itraconazole 200mg QD on 8th day, itraconazole 200mg QD on 9th day; Period 3: 3 days rabeprazole 20mg BID, IMP+rabeprazole 20mg QD on 4th day; Period 4: 9 days rifampicin 600mg QD, IMP on 10th day

PROGRAM PATH: X:\~\QSC200311\~\TFLS\PRODUCTION\TAB XX

DDMMMYYYY HH:MM

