# Appendix 1 Part 1 Study Flow Chart

Footnotes on next page

a Morning of Periods 1, 2 and 4, evening of Period 3

b A follow-up visit will take place 3 to 5 days post-final discharge

c Weight only at admission

d Itraconazole on Day 3 (of Period 1; or Day -7 of Period 2 if washout period is extended) and continuing from Day -6 to -1 (Period 2); rabeprazole from Day -3 to -1 (Period 3); rifampicin from Day -9 to -1 (Period 4). On Day -1, subjects will take itraconazole (Period 2) and rifampicin (Period 4) in the clinic after admission, and rabeprazole (Period 3) at home prior to admission.

• IMP will be administered in the fed state. Co-administration with NIMP in Periods 2 and 3; itraconazole will be administered at the same time as IMP in Period 2 (fed state) and rabeprazole will be administered approximately 2 h prior to IMP in Period 3 (fasted state)

f Haematology and clinical chemistry; virology and creatinine clearance at screening only

 Day -3 (Period 3) and Day -5 (Period 4) only

h Periods 1, 2 and 4 only

i Twelve-lead ECGs will be measured after the subject has been in the supine position for a minimum of 5 min. Single ECGs will be measured at all time points with the exception of pre-dose and 4 h post-dose on Day 1 of each study period, during which times ECGs will be measured in triplicate, a minimum of 2 min apart j Blood pressure, heart rate and oral temperature

	S	0											P	eri	ods	1 a	nd 2													[
			Aª										Re	sid	lent	in (	Clini	>											D	FUP®
Study Day	-28 to	-3	-1	1 2														2	3	6-8										
	-2	(Period 2)		Pre- dose						-			Tim	ie F	Rela	tive	e to M	(D0)	25 Do	sin	g (h	)								
					0	0.5	1	1.5	2	3	4	5	6	8	10	12	12.	5 13	13.5	14	15	16	17	18	20	22	24	36	48	
General Assessments						· · · · ·																								
Informed Consent	X																													
Medical History	X		Х						Γ																					
Weight and Height	X		Xc						Ι									Τ												
Vein Assessment	X																													
CO Breath Test	X		Х											Γ	Τ	Τ														
Drug Screen	X		X						ŀ			1			Τ					Γ	 									
Alcohol Breath Test	X		X																											
Non-IMP Administration d		Xq	Xq	Xq																										
IMP Administration e					X	1										X														
Safety Assessments										1										1 1 1 -						· · · · ·	,			

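### AEs that start on co-medication alone, before that period's KD025 dose, are tabulated under KD025 + NIMP, and no planned AE summary separates them

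*SAP*

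**What the plan says.** SAP 10.4 anchors treatment-emergence once per study part. TEAEs are "AEs that commence during/after the first dose of IMP (ie Period 1"), plus earlier events that worsen on IMP or NIMP. The column is then chosen by period: "TEAEs will be assigned to the period in which the AE first occurred". Washout events are the one group sent backwards: "AEs that occur during the washout period will be assigned to the treatment the subject received during the period immediately before the washout period". For events before the Period 1 KD025 dose, SAP 10.4.1 says "All pre-dose AEs (as defined in Section 10.4) will be excluded from the summary tables", although they are listed.

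SAP 3.2.2, Table 1, fixes how periods, days and treatments are reported. It places the NIMP-only days in the KD025 + NIMP rows:
- rabeprazole: Days -3 to -1
- rifampicin: Days -9 to -1
- itraconazole: from "Day 3 (Period 1; or Day -7 of Period 2 if washout period is extended"), then Days -6 to -1
- omeprazole: from Day 3 of Period 1 (or Day -3 of Period 2), then Days -2 and -1

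For exposure, mock Table 14.1.1.5 follows the same layout, with the note that "the first time-point for the second treatment may be changed from Day 3, Period 1 to Day -7, Period 2".

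The AE mock tables (14.3.1.1 to 14.3.1.7) have columns for KD025 alone and for KD025 with each NIMP. None has a NIMP-alone column. Under SAP 10.4.1 percentages are based on the number of subjects dosed in the period.

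**The concern.** The secondary objective of each part is the safety and tolerability of KD025, and Table 14.3.1.1 sets the reference and combination columns side by side. A reader will take the combination column to describe KD025 given with the NIMP. Part of it describes the NIMP before KD025 has been given in that period.

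The overlap matters most for liver events. Protocol 6.4.1 names raised ALT and AST as the commonest KD025 events, and Protocol 6.4.2.1 and 6.4.2.3 name hepatic risks for itraconazole and rifampicin. Safety labs are scheduled on NIMP alone. SAP Appendix 1 puts outpatient draws on "Day -3 (Period 3) and Day -5 (Period 4) only" and admission draws on Day -1 of Periods 1, 2 and 4. Protocol 14.5.6 adds: "Any clinically significant abnormality, including changes from baseline, must be reported as an AE". A clinically significant result on Day -5 of Period 4, in a subject who later takes KD025 in that period, would be counted under KD025 + rifampicin although it arose on rifampicin alone.

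**Working it through.** **1. Do lead-in AEs reach the combination column?** They start after the Period 1 KD025 dose, so they are TEAEs. They are not washout events, because washout ends when the NIMP starts. SAP 5.1.2 says so for omeprazole. SAP 5.1.1 implies it for Part 1, where a 2-day washout leads to itraconazole on Day 3. Days -9 to -1 of Period 4, Days -3 to -1 of Period 3, Days -6 to -1 of Period 2 (Part 1) and Days -2 to -1 of Period 2 (Part 2) carry the test period's own label, so assignment by period puts their AEs under KD025 + NIMP.

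**2. Reproduce the plan's lead-in figures** (no Day 0). Rabeprazole Days -3 to -1 = 3. Rifampicin Days -9 to -1 = 9. Itraconazole Day 3 of Period 1 (standing for Day -7) plus Days -6 to -1 = 1 + 6 = 7. Omeprazole Day 3 of Period 1 (standing for Day -3) plus Days -2 and -1 = 1 + 2 = 3. These match Table 1. The Day 3 dose is the uncertain one: by label it lies in Period 1, while Table 1 lists it with the next treatment. Days certain under either reading are therefore itraconazole 6 and omeprazole 2.

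**3. Calendar at minimum washout** (elapsed days, Period 1 KD025 = 0). Inputs are the minimum washouts of 2, 8 and 4 days in Part 1 and 2 days in Part 2, and follow-up three to five days after the last discharge.
- Part 1: first itraconazole 2; Period 2 KD025 2 + 7 = 9; last itraconazole 10; first rabeprazole 10 + 8 = 18; Period 3 KD025 21; first rifampicin 21 + 4 = 25; Period 4 KD025 34; discharge 36; follow-up 39–41.
- Part 2: first omeprazole 2; Period 2 KD025 5; discharge 7; follow-up 10–12.

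**4. AE window per column**, with Day 3 counted with the next treatment and the last column run to follow-up. Share = days before KD025 / window.

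| Column | Window (days) | Before KD025 | Share |
|---|---|---|---|
| KD025 alone (each part) | 2 − 0 = 2 | 0 | 0% |
| + itraconazole | 18 − 2 = 16 | 7 | 7/16 = 43.8% |
| + rabeprazole | 25 − 18 = 7 | 3 | 3/7 = 42.9% |
| + rifampicin | 39 − 25 = 14 to 41 − 25 = 16 | 9 | 9/14 = 64.3% to 9/16 = 56.3% |
| + omeprazole | 10 − 2 = 8 to 12 − 2 = 10 | 3 | 3/8 = 37.5% to 3/10 = 30.0% |

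**5. Literal reading of Day 3 as Period 1.** One day moves from the itraconazole and omeprazole windows to KD025 alone. Itraconazole becomes 6/15 = 40%, and omeprazole 2/7 = 29% to 2/9 = 22%. The KD025-alone window becomes 3 days, 1 of them after a NIMP dose. The misattribution then also reaches the reference column.

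**6. Doses taken before scheduled draws on NIMP alone.** Period 4 Day -5: at least 4 rifampicin doses (Days -9 to -6). Period 4 Day -1: at least 8 (Days -9 to -2). Period 2 Day -1: at least 6 itraconazole doses (Day 3 of Period 1, then Days -6 to -2, 1 + 5).

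The documents give no AE rate and none is assumed. The shares are of calendar time, not of events.

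**The case against.** The strongest reply is that the liver data are already protected. SAP 10.5.1 takes the laboratory baseline at Day -1 admission in Periods 2 and 4, after at least 6 of the 7 itraconazole and 8 of the 9 rifampicin lead-in doses. Change from baseline and shift tables run from there to 48 h after KD025. In Part 2 the laboratory baseline is Day 1 pre-dose, and vital signs and ECGs use Day 1 pre-dose throughout (10.6.1, 10.7.1). This stands, with one exception: the Period 3 laboratory baseline is Day -3. It confines the problem to AE counts.

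Second, the labels are regimen labels and the Part 1 mock tables footnote the dosing sequence. ADR tables, tables by relationship to IMP and to NIMP, and full TEAE and dosing listings are also planned. These mitigate in part. However, a footnote gives the dosing order, not AE onset. Relationship is open-label investigator judgement shown under the same columns. Listings leave the reader to rebuild the split.

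Third, a NIMP-alone window follows earlier KD025 doses, so it cannot exclude a delayed KD025 effect. Protocol 5.3.2 says earlier liver events generally appeared after 16 to 36 days of KD025. That is a fair reason not to make a 48-hour comparison the main display. It does not justify merging onset before and after the dose.

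Two stronger inferences fail. A reader might call the rule uneven, because AEs before KD025 are excluded in Period 1 but counted later. The documents do not support this: SAP 3.2.2 treats the NIMPs as study drugs, and no study drug precedes KD025 in Period 1 of a part, whereas the later lead-in days follow KD025 and are on a NIMP. A reader might also infer that a subject withdrawn on rifampicin alone would appear in the KD025 + rifampicin withdrawal row. SAP Section 10 groups by what was actually received and 10.4.1 uses subjects dosed in the period; neither says where that subject goes. The column is undefined.

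**Conclusion.** The point holds for the AE summary tables. Followed as written, SAP 10.4 with Table 1 counts AEs from 3 rabeprazole-only, 9 rifampicin-only, at least 6 itraconazole-only and at least 2 omeprazole-only days as KD025 + NIMP events. The last two rise to 7 and 3 if Day 3 of Period 1 goes with the next treatment. It would be too strong to treat 7 and 3 as settled at minimum washout; they are unambiguous only if the washout is extended and the first dose moves to Day -7 or Day -3 of Period 2.

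The shares of 44%, 43%, 56–64% and 30–38% assume minimum washouts, Day 3 counted with the next treatment, and the last column run to follow-up. Stopping at discharge would give a more striking 9/11 = 82% for rifampicin and 3/5 = 60% for omeprazole. Protocol 14.3 records AEs to the follow-up visit, so those figures are not relied on. Longer washouts would change the window lengths and shares but would not move the lead-in days to after KD025.

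The effect is limited to descriptive AE tables for the secondary objective. PK conclusions are unaffected, and no excess of AEs is shown or implied. The change is worth making before the tables are produced.

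**What to change.** In SAP 10.4 and 10.4.1, split the TEAEs of each test period by onset:
- **NIMP alone:** from the first NIMP dose to just before that period's KD025 dose.
- **KD025 + NIMP:** from that KD025 dose onward.

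Use the subjects entering each window as the denominator, and keep the all-TEAE table.

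State three boundary rules:
- AEs after the first NIMP dose on Day 3 of Period 1 go to the next treatment's NIMP-alone window.
- AEs after the final discharge go to the last treatment.
- A subject who takes the NIMP but not KD025 in a period is counted only under NIMP alone for that period.

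A common 0–48 h post-KD025 display across all columns is an optional supplement.

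No new procedures are needed: AE onset date and time (Protocol 14.3) and dosing dates and times (SAP 10.2) are already recorded. Where onset is only partly known, the file note that SAP 10.4 already requires for the period can also record the window. The cost is SAP wording, extra columns and small counts per cell.

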#### Part 1

- Day -28 to Day -2 of Period 1 (Screening)
- Outpatient Visits (Day -3, Period 3; Day -9, Period 4; and Day -5, Period 4)
- Day -1 (Admission) and Day 1 through to Day 3 (Discharge) for each period
- Follow-up (3 to 5 days post-final discharge)

#### Part 2

Day -28 to Day -2 of Period 1 (Screening)

Reporting and Analysis Plan KD025-107 (QSC200311) Final v2.0 09 Nov 2018 Page 10 of 99

- Outpatient Visit (Day -3, Period 2)
- Day -1 (Admission) and Day 1 through to Day 3 (Discharge) for each period
- Follow-up (3 to 5 days post-final discharge)

Time points within these days are detailed in the schedule of assessments in Appendix 1 for Part 1 and in Appendix 2 for Part 2.

Baseline is defined as nominally the last measurement recorded prior to the first dose of investigational medicinal product (IMP) in each study period. These will be defined for each safety endpoint in the relevant reporting sections.

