# 10.4.1.5 Summary of Treatment-Emergent Adverse Events by Relationship to NIMP

All subjects reporting TEAEs will be summarised by relationship to NIMP (ie unrelated, possibly related and related) and treatment (Periods 2 to 4 of Part 1 and Period 2 of Part 2 only). Counts will be given for number of subjects, not number of events. Counts will be given by the closest relationship to NIMP (ie subjects experiencing more than 1 TEAE within a period will be counted only once using the most closely related event).

Additionally, subjects reporting TEAEs will be summarised for SOC and PT by closest relationship to NIMP (ie unrelated, possibly related or related) and treatment. Counts will be given for total number of subjects, not for events. Counts by closest relationship will be given (ie subjects experiencing more than 1 TEAE within a period will be counted only once within each SOC and PT using the most closely related event).

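### On the default schedule the SAP gives two answers on where to count an adverse event that starts on Day 3 of Period 1 after the first itraconazole or omeprazole dose

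*SAP*

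**What the plan says.** SAP 10.4 sets the general rule: "TEAEs will be assigned to the period in which the AE first occurred". It adds a washout rule: "AEs that occur during the washout period will be assigned to the treatment the subject received during the period immediately before the washout period". SAP 3.2.3 lists the visits in both parts as "Day -1 (Admission) and Day 1 through to Day 3 (Discharge) for each period", so Day 3 belongs to the period whose KD025 dose was given on Day 1. Period 1 is KD025 alone in both parts.

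SAP 3.2.2 makes Table 1 the reference for labels: "Throughout the reporting of the study, period, day and treatments will be reported as detailed in Table 1 below". In the Part 2 row for Period 2 (KD025 plus omeprazole), omeprazole is shown as "Starting on Day 3 (Period 1, or Day -3 of Period 2 if washout period is extended"). The Part 1 row for itraconazole is built the same way, with Day -7 as the alternative. The note under mock exposure Table 14.1.1.5 says that, with an extended washout, "the first time-point for the second treatment may be changed from Day 3, Period 1 to Day -7, Period 2".

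SAP 10.4.1.5 limits the tables of relationship to NIMP to "treatment (Periods 2 to 4 of Part 1 and Period 2 of Part 2 only"). SAP 10.4.1 takes the percentage denominator as the "number of subjects dosed in each period, shown in TABLE 14.1.1.1".

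**The concern.** The dose and an event that follows it on the same day can be reported in different columns: the dose under the combination, the event under KD025 alone. An event that the investigator judged related to itraconazole or omeprazole would then be missing from the table meant to show such events. The column would also depend on scheduling. If the washout is extended, the same first dose falls on Day -7 (itraconazole) or Day -3 (omeprazole) of Period 2, and the same event goes to the combination.

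Safety and tolerability of KD025 is the secondary objective of both parts, and the KD025-alone column is what the combinations will be compared with. Same-day events are plausible. Protocol 6.2.5 has omeprazole peaking within 1 to 2 h. The common side effects given in Protocol 6.4.2 for itraconazole (nausea, rash) and omeprazole (headache, nausea, diarrhoea) are also commonly reported with KD025 (Protocol 5.3.2). A reader of the table could not tell them apart.

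**Working it through.** The plan states no figure to reproduce. The check sets the provisions side by side and then sizes one event.

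**1. Which dose is at issue.** Table 1 has 7 days of itraconazole before KD025 in Period 2. Day -6 to Day -1 is 6 days, so 7 − 6 = 1 dose is the one on Day 3 of Period 1. It has 3 days of omeprazole before KD025. Day -2 and Day -1 are 2 days, so 3 − 2 = 1 dose is the one at Period 1 discharge. That is 1 of 9 itraconazole days and 1 of 4 omeprazole days.

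**2. The two readings.**

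| Points to KD025 alone | Points to the combination |
|---|---|
| Table 1 labels the day as Day 3 of Period 1 | Table 1 places the dose in the Period 2 combination row |
| SAP 3.2.3 puts Day 3 in the period just dosed | Mock Table 14.1.1.5 counts the itraconazole dose under KD025 plus itraconazole |
| SAP 10.4 assigns by period of onset | Footnotes to the Part 1 adverse event mock tables give Period 2 as starting with 7 days of itraconazole |
| SAP 10.4.1.5 leaves out Period 1 | Period tables in Protocol 8.1.1 and 8.1.2 count 7 and 3 lead-in days in Period 2; Protocol 11.1.2 dates all omeprazole doses within Period 2 |

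SAP section 10 presents safety by actual treatment received in each period. That is still organised by period and does not say when Period 2 begins.

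**3. The washout rule.** It does not break the tie. In Part 2, Protocol 8.1.2 and SAP 5.1.2 define the washout as running from Period 1 dosing to the start of omeprazole, so time after that dose is not washout. In Part 1 the minimum is 2 days after dosing on Day 1, which is used up by Day 3.

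**4. The other lead-ins.** Rabeprazole starts on Day -3 of Period 3 and rifampicin on Day -9 of Period 4. Events after those first doses fall in the test period without dispute.

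**5. Size per affected subject.** Take a subject with no other event in that table row in either column. Use the planned 40 and 38 subjects for Period 1 and assume that between 34 (the evaluable target) and all planned subjects are dosed in Period 2.

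- KD025-alone column: 1/40 = 2.5 points (Part 1); 1/38 = 2.6 points (Part 2).
- Combination column: 1/40 = 2.5 to 1/34 = 2.9 points (Part 1); 1/38 = 2.6 to 1/34 = 2.9 points (Part 2).
- Difference between columns: 2.5 + 2.5 = 5.0 to 2.5 + 2.94 = 5.4 points (Part 1); 2.63 + 2.63 = 5.3 to 2.63 + 2.94 = 5.6 points (Part 2).

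**6. KD025 left at the first NIMP dose.** Protocol 5.3.2 gives a typical half-life of 4 to 8 h. Part 1: 48/8 = 6 to 48/4 = 12 half-lives, or about 1.6% to 0.02% by simple halving. Part 2, from the evening dose: 48 − 12 = 36 h, so 36/8 = 4.5 to 36/4 = 9 half-lives, or about 4.4% to 0.2%. A few half-lives above 8 h are reported, so these are typical values only.

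**7. Denominator.** If a subject counts as dosed in a period only on receiving KD025, anyone who has an event during a NIMP lead-in and leaves before KD025 could be in the numerator but not the denominator. This applies to all four lead-ins, not only to Day 3.

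**The case against.** The strongest reply is that the plan's intent is already clear. The footnotes on the Part 1 adverse event mock tables cannot reach 7 itraconazole days in Period 2 without the Day 3 dose, and the Protocol speaks of omeprazole dosing as starting in Period 2. On that view the Period 1 tag is a loose calendar label, and an event after the dose already belongs to the combination. This stands in part. A reader might infer that SAP 10.4 definitely places these events under KD025 alone, with the washout rule as confirmation. The documents do not support that: the literal chain leads there, but other provisions lead the other way, and the washout rule does not apply after the first omeprazole dose. The reply still does not remove the conflict, because Table 1 itself dates the dose to Period 1 and SAP section 15 calls the mock tables illustrative.

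A second reply is that neither column is plainly right for an event hours after a first NIMP dose, with no KD025 that day and some KD025 perhaps remaining. That also stands: the choice is a convention. It should nonetheless be stated, and be the same for every lead-in.

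A third is that little is at stake, since all TEAEs and dose times are listed. That is true, and it limits the weight of the point.

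**Conclusion.** The contradiction is real on the default schedule and disappears if the washout is extended. It covers the remainder of Day 3 after the dose, under 24 h per subject, and touches only descriptive adverse event tables. The 5.0 to 5.6 points are what one affected subject contributes when moved between columns, under the assumptions on numbers dosed given above. They are not an estimate of bias: a reader might infer that the KD025-alone column is too high by a known amount, but the number of affected subjects is unknown and the plan does not settle which column is right. The PK conclusions are unaffected. This is a low-cost clarification worth making before database lock.

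**What to change.** In SAP 10.4, add: For adverse event reporting, each test treatment starts at the date and time of its first NIMP dose, including a dose taken on Day 3 of Period 1. A TEAE starting at or after that time is assigned to that test treatment and included in the NIMP-relationship tables.

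In SAP 10.4.1, add: The denominator for each test treatment is the number of subjects who received at least one dose of NIMP or KD025 for that treatment. Footnote Table 14.1.1.1, and its Part 2 counterpart 14.1.2.1, to match. This agrees with SAP 6.1, where any study drug, NIMP included, qualifies a subject for the safety population.

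The cost is a few sentences and a footnote. Onset date and time (Protocol 14.3) and the date and time of every dose (SAP 10.2) are already recorded, and SAP 10.4 already covers missing or partial onset times. No visit, sample, dose or PK analysis changes. The downside is that a late KD025 reaction starting after the Day 3 dose would appear under the combination. Its relationship to KD025 is still classified, so it would still be reported as an adverse drug reaction.
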